Appendix B: Contraceptive Guidelines and Pregnancy

Women Not of Childbearing Potential are defined as Follows

Women are considered post-menopausal and not of child-bearing potential if they have had 12 months of natural (spontaneous) amenorrhea with an appropriate clinical profile (e.g., age appropriate, history of vasomotor symptoms) or have had surgical bilateral oophorectomy (with or without hysterectomy) at least six weeks ago. In the case of oophorectomy alone, only when the reproductive status of the woman has been confirmed by follow up hormone level assessment is she considered not of child bearing potential.

Contraceptive Guidelines for Women of Child-Bearing Potential

Women of child-bearing potential, defined as all women physiologically capable of becoming pregnant, must use highly effective contraception during the study and for 30 days after the last dose of study drug. The highly effective contraception is defined as either:

- 1. True abstinence: When this is in line with the preferred and usual lifestyle of the patient. Periodic abstinence (e.g., calendar, ovulation, symptom-thermal, post-ovulation methods) and withdrawal are not acceptable methods of contraception.
- 2. Sterilization: have had surgical bilateral oophorectomy (with or without hysterectomy) or tubal ligation at least six weeks ago. In case of oophorectomy alone, only when the reproductive status of the woman has been confirmed by follow up hormone level assessment.
- 3. Male partner sterilization (with the appropriate post-vasectomy documentation of the absence of sperm in the ejaculate). For female patients on the study, the vasectomized male partner should be the sole partner for that patient.
- 4. Use of a combination of any two of the following (a+b):
 - a. Placement of an intrauterine device (IUD) or intrauterine system (IUS).
 - b. Barrier methods of contraception: Condom or Occlusive cap (diaphragm or cervical/vault caps) with spermicidal foam/gel/film/cream/vaginal suppository/pessary.

The following are unacceptable forms of contraception for women of childbearing potential:

- Oral contraception, injected or implanted hormonal.
- IUD progesterone T
- Female condom
- Natural family planning (rhythm method) or breastfeeding
- Fertility awareness
- Withdrawal
- Cervical shield

Women of child-bearing potential must have a negative serum or urine pregnancy test ≤ 72 hours prior to initiating treatment.

Pregnancies

CONFIDENTIAL Page 64 of 66

To ensure patient safety, each pregnancy in a patient on study treatment must be reported to Rhizen Pharmaceuticals AG within 24 hours of learning of its occurrence. The pregnancy should be followed up for 3 months after the termination of the pregnancy to determine outcome, including spontaneous or voluntary termination, details of the birth, and the presence or absence of any birth defects, congenital abnormalities, or maternal and/or newborn complications. Consent to report information regarding these pregnancy outcomes should be obtained from the mother.

Pregnancy is not considered a SAE. Initial and follow up information should be recorded on a Clinical Study Pregnancy Form and reported by the investigator to Rhizen Pharmaceuticals AG. Pregnancy follow-up should be recorded on the same form and should include an assessment of the possible relationship to the investigational drugs to any pregnancy outcome will also be captured on the pregnancy form. Any SAE experienced during pregnancy must be reported on the SAE Report Form.

Pregnancy outcomes must be collected for the female partners of any males who took study treatment in this study. Consent to report information regarding these pregnancy outcomes should be obtained from the mother.

CONFIDENTIAL Page 65 of 66

Appendix C: Cytokines/Chemokines and Tumour Biopsy

• Serum samples will be assessed for following cytokines/chemokines at the screening (baseline) and at Cycle 3 Day 1:

| Assessment | Tissue sample | Exploratory marker |
|-----------------------------------|----------------------|---|
| Cytokines/Chemokines | Serum | CCL2/JE/MCP-1, CCL3/MIP-1alpha, CCL4/MIP-1 beta, CCL11/Eotaxin, CCL13/MCP-4, CCL17/TARC, CCL22/MDC, CCL26/Eotaxin-3, CXCL9/MIG, CXCL10/IP-10/CRG-2, IL-8/CXCL8 IFN-γ, IL-1β, IL-2, IL-4, IL-6, IL-8, IL-10, IL-12p70, IL-13, TNF-α |
| Gene expression by RNA sequencing | Tissue biopsy sample | Approx. 21,000 genes |

CONFIDENTIAL Page 66 of 66

1. LIST OF ABBREVIATIONS AND DEFINITIONS OF TERMS

Table 1: Abbreviations and Definitions of Terms

Add or remove as necessary

AE(s)	adverse event(s)	
b.i.d.	twice daily	
BUN	blood urea nitrogen	
CI	confidence interval	

CR	Complete response
CRF	case report form
ECG	electrocardiogram
FDA	
HDL	Food and Drug Administration
HEENT	high-density lipoprotein
	head, eyes, ears, nose, and throat
HIV	human immunodeficiency virus
ICH	International Council for Harmonisation
IRB/IEC	Institutional Review Board/Independent Ethics Committee
ITT	intent-to-treat
LDH	lactate dehydrogenase
LDL	low-density lipoprotein
MedDRA	medical dictionary for regulatory activities
mg	milligram
n	number of patients
PR	Partial response
QTc	Q-T interval corrected for heart rate
QTc-F	Q-T interval corrected for heart rate using Frederica's formula
SAE	serious adverse event
SAS®	(statistical analysis software)
SD	Stable disease
SOC	system organ class
TEAE	treatment-emergent adverse event
WHO	World Health Organisation

2. INTRODUCTION

This statistical analysis plan (SAP) contains definition of analysis population(s), derived variables and statistical methods for efficacy and safety analysis.

The SAP is written based on the following documentation:

Document	Date	Version	
Protocol	29June2021	1.0	
eCRF	24Sep2021	1.0	
eCRF	16June2022	5.0	

Breast cancer is the most common cancer diagnosed in women and is the second leading cause of cancerrelated deaths. Based on these pre-clinical evidences with tenalisib and clinical evidences from other PI3K inhibitors, it is proposed that tenalisib has the potential to treat the patients with locally advanced and metastatic breast cancer.

The objective of the study is to assess the anti-tumour activity along with safety and efficacy of tenalisib at two different doses in order to identify the optimal dose that shows signal of clinical efficacy with an acceptable safety profile. This dose can be thus taken ahead for further development. Doses of 800 mg BID and 1200 mg BID are proposed in this Phase II study.

3. STUDY OBJECTIVES

Primary Objective

To assess the anti-tumour activity of tenalisib in patients with locally advanced or metastatic breast cancer.

Secondary Objective

Document Date: 12MAY2023

Page 4 of 106 ST-AD-032 version 01

To evaluate the safety and tolerability of tenalisib.

Exploratory Objective

Changes in serum cytokines/chemokines and tumour tissue gene expression post treatment with tenalisib.

[figure not shown]
4. STUDY DESIGN

4.1 General Design

This is a Phase II, randomized, open label study, designed to evaluate the preliminary efficacy and safety of tenalisib at two dose levels (800 mg BID and 1200 mg BID) in 40 patients with locally advanced or metastatic breast cancer. Twenty patients each, will be enrolled in Group 1 (Tenalisib 800 mg BID) and Group 2 (Tenalisib 1200 mg BID). Both groups will run in parallel. The expected duration of patient participation in the study will be approximately 24 months, unless the patient is discontinued from the study due to disease progression, drug toxicity or consent withdrawal.

4.2 Discussion of Study Design

The study design flow chart is as follows:

Note:

4.3 Method of Assignment of Patients to Treatment Groups

This is a randomized, open label study. Eligible patients will be randomized to one of the two groups (Group 1: Tenalisib 800 mg BID and Group 2: Tenalisib 1200 mg BID) in 1:1 ratio based on the central randomization list generated by a validated software.

4.4 Blinding

Document Date: 12MAY2023

Blinding is not applicable as this is an open label study.

Page 5 of 106 ST-AD-032 version 01

^{*} Disease will be re-assessed at C3D1 (± 7 days) and approximately 8 weeks thereafter (± 7 days), and/or at the EOT and/or as clinically indicated (if clinical progression is suspected).

^{**} Patients will undergo the end-of-treatment (EOT) assessments within 7 days after last dose of study drug or discontinuation.

4.5 Determination of Sample Size

A sample size of 20 per group will provide a precision of 13% for a two-sided 90% confidence interval based on Exact (Clopper-Pearson) method assuming the percentage of patients without progression at the end of 6 months is 20%. Thus, a total of 40 patients (20 patients in each group) will be enrolled in the study.

CHANGES IN THE CONDUCT OF THE STUDY OR PLANNED ANALYSES 5.

5.1 Changes in the Conduct of the Study

The study was planned to administer tenalisib to all patients until disease progression or unacceptable toxicity for a maximum duration of 24 months. However this was changed and the study was closed earlier before all patients in the study showed disease progression. .

5.2 Changes from the Analyses Planned in the Protocol

There were no changes in the analysis planned in the protocol of the study at the time of preparing this statistical analysis plan.

BASELINE, EFFICACY and Safety EVALUATIONS 6.

6.1 Schedule of Evaluations

The assessments to be conducted at each scheduled visit are displayed in the following table.

Table 1 **Assessments Conducted at each Scheduled Visit**

Table 5 : Schedule of Events										
Cycle	Screening	C1		C2		C3	Monthly visits (C4 onward up to 2 year) ¹⁹	Efficacy Visits (C5, C7, C9 up to 2 year) ²⁰	EOT ²¹	EOS ²²
Day	D-28 to 0	D1	D15	D1	D15	D1	D1	D1	-	-
Window period	-		±1	±1	±3	±3	±3	±7	+7	+30
Study Days	D-28 to 0	1	15	29	43	57	-	-	-	-
Informed Consent ¹	X	-	-	-	-	-	-	-	-	-
Demographics ²	X	-	-	-	-	-	-	-	-	-
Medical history ³	X	Χ	-	-	-	-	-	-	-	-
Vitals ⁴	X	Χ	Χ	Χ	Χ	Χ	X	-	Χ	-
Height and weight⁵	X	Χ	Χ	Χ	Χ	Χ	X	-	Χ	-
Physical examination ⁶	X	Χ	Χ	Χ	Χ	Χ	X	-	Χ	-
ECOG Performance Status	X	Х	-	Х	-	-	X	-	X	-
Complete blood count ⁷	Х	Х	Х	Х	Х	Х	Х	-	Х	-
Chemistry panel I8	Х	Χ	Х	Χ	Х	Χ	Χ	-	Х	-
Chemistry panel II ⁹	Х	Χ	-	Χ	-	Χ	Х	-	Х	-

CONFIDENTIAL Document Date: 12MAY2023 ST-AD-032 version 01

HIV, HBV, HCV status	X	1_		1_	_	_	_	_	1_	1_
PT and INR ¹⁰	X	X	-	X	 	X	-	_	X	
Cytokines/chemokines analysis ¹¹	X	-	-	-	-	X	-	-	-	-
Urinalysis (routine)	Χ	Х	Х	Х	Х	Х	Χ	-	Х	-
Pregnancy test ¹²	Χ	Х	-	-	-	-	-	-	-	-
12-lead ECGs ¹³	Χ	Х	-	Χ	-	Х	-	-	Х	-
Tumour biopsy ¹⁴	Χ	-	-	-	-	Х	-	-	-	-
Radiological	Χ	-	-	-	-	Х	-	X	Х	-
assessment (CT and/or MRI) ¹⁵										
Bone scan ¹⁶	Χ	-	-	-	-	-	-	-	-	-
Drug Dispensing ¹⁷	-	X	-	Χ	-	Х	Χ	-	-	-
Tenalisib	-	Х	Х	Х	Х	Х	Χ	-	-	-
administration ¹⁸										
Drug compliance	-	Х	Х	Χ	Х	Х	Χ	-	Х	-
AE evaluation	Χ	Х	Х	Х	Χ	Х	Х	-	Х	Х
SAE evaluation	Χ	X	Х	Χ	Χ	Х	Х	-	X	Х
Concomitant medication	Х	Х	Х	Х	Х	Х	Х	-	Х	Х

Footnotes:

- 1. Patient should be re-consented, if informed consent is obtained > 30 days prior to the initiation of trial treatment. The first day of tenalisib administration will be considered as C1D1.
- 2. Demographic profile will include age, sex and race.
- 3. Detailed history will be taken at screening that includes history of cancer, past history, no of prior therapies and prior medication (in last 4weeks); and other medical history. Patient's medical record must include prior treatments received, dates of administration, response to prior therapies and date of progression.
- 4. Vitals will include pulse (sitting/supine); blood pressure (sitting/supine); respiratory rate and oral temperature. Vitals will be done at pre-dose at all visits.
- 5. Weight will be measured at all visits. Height to be measured at screening only.
- 6. Physical examination will include systemic examination (General Appearance, HEENT, neck, cardiovascular, lungs, abdomen, extremities, neurological, skin, and musculoskeletal). Complete physical examination will be done at screening visit. At subsequent visits, abbreviated examination will be done depending on the assessment of tumour.
- 7. This will include Hb, complete blood count, total leucocyte and differential count and platelet count. Additional investigations will be performed if clinically indicated. Hematology must be done ≤ 7 days prior to initiation of treatment. However, if these initial examinations are obtained within 72 hours of C1D1; they do not have to be repeated.
- 8. Chemistry Panel I include blood glucose, albumin, total protein, total bilirubin, ALP, AST, ALT, GGT, LDH, urea or blood urea nitrogen, creatinine, sodium, potassium, chloride, calcium, phosphorus. These tests must be done ≤ 7 days prior to initiation of treatment. However, if these initial examinations are obtained within 72 hours of C1D1; they do not have to be repeated. These tests will be performed at supplementary visits if clinically indicated.
- 9. Chemistry Panel II includes total cholesterol, TG, LDL, HDL, T3, T4 and TSH. These tests must be done ≤ 7 days prior to initiation of treatment. However, if these initial examinations are obtained within 72 hours of C1D1; they do not have to be repeated. These tests will be performed at supplementary visits if clinically indicated.

CONFIDENTIAL Page 7 of 106 ST-AD-032 version 01

- 10. The tests must be done ≤ 7 days prior to initiation of treatment. However, if initial examination is obtained within 72 hours of C1D1; this does not have to be repeated. This test will be performed at supplementary visits if clinically indicated.
- 11. Blood will be collected in all patients for serum cytokine/chemokine estimation at screening (baseline) and at C3D1.
- 12. This is required for women of child-bearing potential. A serum pregnancy test will be performed at screening and 72 hours prior to dosing. Urine pregnancy test will be performed at other visits as indicated.
- 13. ECGs will be performed at screening and C1D1 pre-dose to establish baseline cardiac activity. Additional ECGs will be obtained if clinically indicated. All ECGs will be performed on local equipment.
- 14. A tumour biopsy will be performed in 10-12 patients who have consented for the biopsy. The biopsy will be done after eligibility confirmation prior to the first dose on C1D1. A second tumour biopsy sample will be taken at C3D1.
- 15. CT and/ or MRI will be performed at the time of screening within 28 days of screening. Disease will be re-assessed at C3D1 (± 7 days) and approximately 8 weeks thereafter (± 7 days), and/or at the EOT (not required if done within last 28 days) and/or as clinically indicated (if clinical progression is suspected). If a CR or PR is noted, confirmatory scans should be performed at least 4 weeks after the initial response was first documented. Tumour imaging should remain consistent throughout the study and should include those thought by investigator to best capture status of disease. (Baseline scan, if already available as SOC within 28-days of screening is accepted as part of study protocol). Any other sites at which new disease is suspected should also be appropriately imaged.
- 16. Bone scan will be done at the baseline when progression in bone is suspected. Bone scans need to be repeated only when complete response is reported in target disease or when progression in bone is suspected.
- 17. Tenalisib will be dispensed in a HDPE container having 30 tablets of tenalisib.
- 18. Tenalisib will be administered orally twice a day in 28-days of cycle. Tenalisib will be continued in patients experiencing clinical benefit for 24 months unless progression of disease or toxicity is observed warranting discontinuation of therapy.
- 19. All visits will be done monthly from Cycle 3 onwards for 24 months (e.g. C4, C5, C6.... C26).
- 20. All visits for efficacy assessments will be done at 8-weekly intervals (± 7 days) for 24 months (e.g.C5, C7.... C26).
- 21. All patients will undergo the end-of-treatment (EOT) assessments within 7 days after last dose of study drug or discontinuation.
- 22. Patients must be followed telephonically for adverse events for 30 calendar days after the last dose of study drug.

6.2 Time Point Algorithms

6.2.1 Relative Day

The date of first dose of study drug will be considered relative day 1, and the day before the first dose of study drug will be relative day -1. Relative days will be calculated as follows only when the full assessment date is known (i.e., partial dates will have missing relative days):

For days on or after the first dose of study drug:

Date of Assessment – Date of First Dose of Study Drug + 1.

For days before the first dose of study drug: Date of Assessment – Date of First Dose of Study Drug.

CONFIDENTIAL Page 8 of 106
Document Date: 12MAY2023. ST-AD-032 version 01

6.2.2 Windows

For the purpose of statistical analysis, the visit numbers will be recalculated in terms of study days since the first day of the trial medication, as illustrated in the following table:

Analysis Windows

Visit	Scheduled Study Day	Visit Window for Analysis (Days)
Screening	-28 to 0	-
C1D1	1	0
C1D15	15	14 – 16
C2D1	29	28 – 30
C2D15	43	40 – 46
C3D1	57	54 – 60
Monthly visits (C4 onward up to	-	±3
2 year)		
Efficacy Visits (C5, C7, C9 up	-	±7
to 2 year)		
EOT	-	+7
EOS	-	+30

EOT=End of Treatment; EOS= End of study; C1D1=Cycle 1 Day 1.

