6.9 End of Study (EOS) Visit

All patients must be followed up telephonically for adverse events for 30 calendar days after the last dose of study drug. In case of drug related SAE/AE or treatment discontinuation due to adverse event, the patients will be followed till the resolution/stabilization of the AE or 30 days after the last study dose whichever is the earlier.

CONFIDENTIAL Page 37 of 66

| Table 5 : Schedule of Events | | | | | | | | | | |
|---|-----------|----|-----|----|-----|----|---|---|-------------------|-------------------|
| Cycle | Screening | (| C1 | Ó | 22 | С3 | Monthly visits (C4 onward up to 2 year) ¹⁹ | Efficacy Visits (C5, C7, C9 up to 2 year) ²⁰ | EOT ²¹ | EOS ²² |
| Day | D-28 to 0 | D1 | D15 | D1 | D15 | D1 | D1 | D1 | - | - |
| Window period | - | | ±1 | ±1 | ±3 | ±3 | ±3 | ±7 | +7 | +30 |
| Study Days | D-28 to 0 | 1 | 15 | 29 | 43 | 57 | - | - | - | - |
| Informed Consent ¹ | X | - | - | - | - | - | - | - | - | - |
| Demographics ² | X | - | - | - | - | - | - | - | - | - |
| Medical history ³ | X | X | - | - | - | - | - | - | - | - |
| Vitals ⁴ | X | X | X | X | X | X | X | - | X | - |
| Height and weight ⁵ | X | X | X | X | X | X | X | - | X | - |
| Physical examination ⁶ | X | X | X | X | X | X | X | - | X | - |
| ECOG Performance Status | X | X | - | X | - | - | X | - | X | - |
| Complete blood count ⁷ | X | X | X | X | X | X | X | - | X | - |
| Chemistry panel I ⁸ | X | X | X | X | X | X | X | - | X | - |
| Chemistry panel II ⁹ | X | X | - | X | - | X | X | - | X | - |
| HIV, HBV, HCV status | X | - | - | - | - | - | - | - | - | - |
| PT and INR ¹⁰ | X | X | = | X | - | X | - | - | X | = |
| Cytokines/chemokines analysis ¹¹ | X | - | - | - | - | X | - | - | - | - |
| Urinalysis (routine) | X | X | X | X | X | X | X | - | X | - |
| Pregnancy test ¹² | X | X | - | - | - | - | - | - | - | - |
| 12-lead ECGs ¹³ | X | X | - | X | - | X | - | - | X | - |
| Tumour biopsy 14 | X | - | - | - | - | X | - | - | - | - |
| Radiological assessment (CT and/or MRI) 15 | X | - | - | - | - | X | - | X | X | - |
| Bone scan ¹⁶ | X | - | - | - | - | - | - | - | - | - |
| Drug Dispensing ¹⁷ | - | X | - | X | - | X | X | - | - | - |

CONFIDENTIAL Page 38 of 66

Version 1.0, Dated June 29, 2021

| Tenalisib administration ¹⁸ | - | X | X | X | X | X | X | - | - | - |
|--|---|---|---|---|---|---|---|---|---|---|
| Drug compliance | - | X | X | X | X | X | X | - | X | - |
| AE evaluation | X | X | X | X | X | X | X | - | X | X |

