- 10. The tests must be done ≤ 7 days prior to initiation of treatment. However, if initial examination is obtained within 72 hours of C1D1; this does not have to be repeated. This test will be performed at supplementary visits if clinically indicated.
- 11. Blood will be collected in all patients for serum cytokine/chemokine estimation at screening (baseline) and at C3D1.
- 12. This is required for women of child-bearing potential. A serum pregnancy test will be performed at screening and 72 hours prior to dosing. Urine pregnancy test will be performed at other visits as indicated.
- 13. ECGs will be performed at screening and C1D1 pre-dose to establish baseline cardiac activity. Additional ECGs will be obtained if clinically indicated. All ECGs will be performed on local equipment.
- 14. A tumour biopsy will be performed in 10-12 patients who have consented for the biopsy. The biopsy will be done after eligibility confirmation prior to the first dose on C1D1. A second tumour biopsy sample will be taken at C3D1.
- 15. CT and/ or MRI will be performed at the time of screening within 28 days of screening. Disease will be re-assessed at C3D1 (± 7 days) and approximately 8 weeks thereafter (± 7 days), and/or at the EOT (not required if done within last 28 days) and/or as clinically indicated (if clinical progression is

CONFIDENTIAL Page 39 of 66

- suspected). If a CR or PR is noted, confirmatory scans should be performed at least 4 weeks after the initial response was first documented. Tumour imaging should remain consistent throughout the study and should include those thought by investigator to best capture status of disease. (Baseline scan, if already available as SOC within 28-days of screening is accepted as part of study protocol). Any other sites at which new disease is suspected should also be appropriately imaged.
- 16. Bone scan will be done at the baseline when progression in bone is suspected. Bone scans need to be repeated only when complete response is reported in target disease or when progression in bone is suspected.
- 17. Tenalisib will be dispensed in a HDPE container having 30 tablets of tenalisib.
- 18. Tenalisib will be administered orally twice a day in 28-days of cycle. Tenalisib will be continued in patients experiencing clinical benefit for 24 months unless progression of disease or toxicity is observed warranting discontinuation of therapy.

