8 ASSESSMENT OF EFFICACY

8.1 Specification of the Efficacy Parameters

Initial disease assessment of patients should be performed within 28 days prior to the first dose of study drug using computed tomography (CT) and/or magnetic resonance imaging (MRI). This scan will be considered as baseline scan. The PI should review baseline scan images to confirm the subject has measurable disease as defined in the inclusion criteria. Scan performed as part of routine clinical management is acceptable for use as the baseline scan if it is of diagnostic quality and performed within 28 days prior to the C1D1, or as approved by the medical monitor if it is out of window period.

Subsequent scan (CT and/or MRI as applicable) should be done at C3D1 (± 7 days) and approximately 8 weeks thereafter (± 7 days), and/ or at the EOT and so on or as clinically indicated (if clinical progression is suspected). If a CR or PR is noted, confirmatory scans should be performed at least 4 weeks after the initial response was first documented. The scan should be reviewed by site investigator/radiologist/designee and tumour response will be assessed according to the revised Response Evaluation Criteria in Solid Tumour guideline (RECIST) version 1.1.[21]

8.2 Images included in the assessment.

A CT with IV contrast will be the primary modality for assessment, unless the patient has an allergy to contrast that cannot be controlled with pre-medications. If patients are unable to receive iodinated CT contrast, the preferred imaging is non-contrast CT of the chest, and MRI of the abdomen and pelvis with contrast. Tumour imaging should remain consistent throughout study and should include those thought by investigator to best capture status of disease. For skin nodules, CT or MRI will be the preferred modality of assessment. Digital photography will not be acceptable as a method of assessment for skin lesions.

8.3 Measurable and non-measurable disease:

Eligibility of lesions for quantitative assessment will be determined at baseline, with target lesions selected from the measurable lesions identified. After baseline, target lesions will always be assessed quantitatively, and non-target lesions will be assessed qualitatively, with no further evaluation of measurability according to these definitions.

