6.4.2 Secondary Efficacy Variables

The best overall response is defined as the best visit response recorded from the start of the treatment until disease progression/recurrence. This data will be summarized using frequency and percentage for

CONFIDENTIAL Document Date: 12MAY2023. ST-AD-032 version 01

Complete Response (CR), Partial Response (PR), Stable Disease (SD), and Progressive Disease (PD) for each treatment group.

- Overall Response Rate (ORR): The percentages of CR+PR will be calculated and presented along with 95% confidence intervals of these percentages.
- Clinical Benefit Rate (CBR): The percentages of CR+PR+SD>=24 weeks will be calculated and presented along with 95% confidence intervals of these percentages.
- Progression Free Survival (PFS): It is defined as time from the first dose of study drug to documented disease progression or death due to any cause. This variable will be analyzed via Kaplan-Meier methodology.

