Visit/	Actual values	Change from baseling	ne Actual values	Change from baseline	Actual values	Change from baseline
Statistics		values		values		values
Baseline						
N	XX		XX		XX	
Mean	x.xxx		X.XXX		X.XXX	
SD	x.xxxx		X.XXXX		X.XXXX	
Median	x.xxx		X.XXX		X.XXX	
Min, Max	X.XX, X.XX		x.xx, x.xx		x.xx, x.xx	
Cycle 1 Day 1						
N	XX	XX	XX	XX	XX	XX
Mean	x.xxx	X.XXX	X.XXX	X.XXX	X.XXX	X.XXX
SD	x.xxxx	X.XXXX	X.XXXX	X.XXXX	X.XXXX	X.XXXX
Median	x.xxx	X.XXX	X.XXX	X.XXX	X.XXX	X.XXX
Min, Max	x.xx, x.xx	X.XX, X.XX	x.xx, x.xx	x.xx, x.xx	x.xx, x.xx	x.xx, x.xx

Continue for all visits and parameters

The baseline measurement is the last pre-treatment measurement taken on or before Cycle 1 Day 1

Only scheduled visits are included in the table.

EOT: End of Treatment; NE: Non-Estimable.

Reference Listing 16.2.x.x

Program: xx.sas Table Generation: ddmmmyyyy hh:mm:ss

Use same format for

Table 14.3.2.2 Descriptive Summary of Biochemistry parameters - Safety Analysis Set

CONFIDENTIAL Page 55 of 106 Document Date: 12MAY2023. ST-AD-032 version 01

Page xx of yy

Table 14.3.3.1 Descriptive Summary of Vital Signs - Safety Analysis Set

Note - Please remove the column for change from baseline.

Add footnote-"Vitals is collected at Pre-dose during treatment visits"

Table 14.3.4.1 Descriptive Summary of ECG - Safety Analysis Set

Document Date: 12MAY2023.

Note - Please remove the column for change from baseline.

Add footnote-"ECG is collected at Pre-dose during treatment visits"

Protocol RP6530-2101 Table 14.3.4.2 Summary of Abnormal ECG results Safety Analysis Set Page xx of yy

		Tenalisib 800 mg BID	Tenalisib 1200 mg BID	Overall
Visit	Criteria	(N=xx)	(N=xx)	(N=xx)
		n (%)	n (%)	n (%)
Baseline	Clinically significant	xx (xx.x)	xx (xx.x)	xx (xx.x)
	Not clinically significant	xx (xx.x)	xx (xx.x)	xx (xx.x)
Cycle 1 Day 15	Clinically significant	xx (xx.x)	xx (xx.x)	xx (xx.x)
	Not clinically significant	xx (xx.x)	xx (xx.x)	xx (xx.x)
Cycle 2 Day 1	Clinically significant	xx (xx.x)	xx (xx.x)	xx (xx.x)
	Not clinically significant	xx (xx.x)	xx (xx.x)	xx (xx.x)
Cycle 2 Day 15	Clinically significant	xx (xx.x)	xx (xx.x)	xx (xx.x)
	Not clinically significant	xx (xx.x)	xx (xx.x)	xx (xx.x)
Cycle 3 Day 1	Clinically significant	xx (xx.x)	xx (xx.x)	xx (xx.x)
	Not clinically significant	xx (xx.x)	xx (xx.x)	xx (xx.x)
Cycle 3 Day 15	Clinically significant	xx (xx.x)	xx (xx.x)	xx (xx.x)
•	Not clinically significant	xx (xx.x)	xx (xx.x)	xx (xx.x)
Continue for all visit	ts			

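### SAP 6.2.2 gives C3D1 one analysis window (day 54–60), but the first on-treatment scan is allowed on day 50–64, so 8 of 15 compliant scan days belong to no visit

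*SAP*

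**What the plan says.** SAP 6.2.2 does not keep the visit label from the case report form. For analysis, "the visit numbers will be recalculated in terms of study days since the first day of the trial medication". Its table gives C3D1 a scheduled day of 57 and a window of 54–60. The only row for efficacy visits (±7 days) names C5, C7 and C9 onward. Rows from C4 onward show no scheduled study day. The section has no rule for a record that falls in no window.

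The scan has its own, wider tolerance. Protocol 8.1 says that scans "should be done at C3D1 (± 7 days) and approximately 8 weeks thereafter (± 7 days"). Footnote 15 to Protocol Table 5 says the same ("Disease will be re-assessed at C3D1 (± 7 days) and approximately 8 weeks thereafter (± 7 days"), and the SAP repeats that footnote under its own schedule in 6.1. In the body of Table 5, however, the C3D1 scan sits in a column whose visit tolerance is ±3 ("Window period | - | | ±1 | ±1 | ±3 | ±3 | ±3 | ±7 | +7 | +30").

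On response, SAP 6.4.2 states: "The best overall response is defined as the best visit response recorded from the start of the treatment until disease progression/recurrence". Protocol 8.5 likewise derives it from the sequence of overall visit responses.

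**The concern.** The SAP applies a clinic-visit tolerance to an assessment that both documents schedule with a wider one. A site can scan on day 62, comply fully with the protocol, and produce a result that the SAP's visit algorithm places nowhere. This is a stated rule that conflicts with the SAP's own schedule, so two programmers could follow the text and produce different outputs.

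At stake is the first on-treatment tumour assessment. Read literally, a scan outside day 54–60 is missing from the C3D1 column of Listing 16.2.6.6 and from Figure 14.2.2.6, which by its title is a by-visit plot. The same doubt reaches best overall response (BOR) and best change from baseline, because both are worded in terms of visits and the SAP does not say whether these are windowed visits or all scans. The overall response rate (ORR) and clinical benefit rate (CBR) are built on BOR.

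**Working it through.** **Inputs.** Nominal days 15, 29, 43 and 57 and the visit tolerances come from Protocol Table 5. The scan tolerance of ±7 comes from Protocol 8.1 and footnote 15. The analysis windows come from SAP 6.2.2. Day 1 is the first dose (SAP 6.2.1), so with undelayed 28-day cycles the first day of cycle k is 1 + 28 × (k − 1), and C3D1 = 1 + 28 × 2 = 57.

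**Reproducing the SAP's figure.** 57 ± 3 = 54–60. The SAP window is exactly the clinic-visit tolerance.

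**Comparison, nominal day ± tolerance.**

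| Assessment | Protocol tolerance | Protocol days | SAP 6.2.2 | Compliant days outside |
|---|---|---|---|---|
| C1D15 visit | ±1 | 14–16 | 14–16 | 0 |
| C2D1 visit | ±1 | 28–30 | 28–30 | 0 |
| C2D15 visit | ±3 | 40–46 | 40–46 | 0 |
| C3D1 visit | ±3 | 54–60 | 54–60 | 0 |
| C3D1 scan | ±7 | 50–64 | 54–60 | 8 of 15 |
| C5 scan | ±7 | 106–120 if C5D1 is day 113 | ±7, no day stated | 0 on that assumption |

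**The C3D1 scan.** Allowed days: 64 − 50 + 1 = 15. Windowed days: 60 − 54 + 1 = 7. Outside: 15 − 7 = 8, namely 50–53 and 61–64, and 8/15 = 53%.

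**Does a neighbouring window catch these days?** No. C2D15 ends on day 46. C4D1 is 1 + 28 × 3 = 85, and 85 ± 3 = 82–88. Both assume undelayed cycles, because the SAP gives no day for C4.

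**Later scans.** If the next scan is timed 8 weeks ± 7 days from the actual C3D1 scan, its earliest day is 50 + 56 − 7 = 99 and its latest is 64 + 56 + 7 = 127. That range runs partly outside 106–120. The documents do not say which anchor applies.

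**Effect on a rate, if BOR is read as windowed.** Percentages in Table 14.2.2.1 use all patients in the group. With 20 treated per group, one patient is 1/20 = 5 percentage points.

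**The case against.** The strongest reply is that little depends on these windows, and most of that reply stands.

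- **Main analyses.** The primary table shell (14.2.1.1) uses a treatment-duration rule of at least 180 days. PFS and duration of response run between dates. Adverse event summaries count patients and events by system organ class and preferred term. None of these uses a visit window.
- **BOR.** A reader might infer that compliant scans are certainly lost from BOR. The documents do not say so. The definition refers to the best response recorded, and the Table 14.2.2.1 footnote reserves the not-evaluated category for patients with no tumour assessment at all after baseline, whether inside a window or not. Even on the windowed reading, ORR changes only if a CR or PR seen at C3D1 is not also recorded at another counted visit. Losing a first scan of SD or PD leaves its numerator and denominator unchanged.
- **Safety data.** A reader might infer that compliant safety data also belong to no visit. The table above shows otherwise: the four fixed post-baseline windows equal the protocol tolerances. Only late or unscheduled measurements fall between windows. The laboratory shell leaves out unscheduled visits on purpose ("Only scheduled visits are included in the table"), and the data are still listed.
- **Gaps between windows.** It is true that 39 of study days 1–60 lie in no window (60 − (1 + 3 + 3 + 7 + 7) = 39, counting C1D1 as day 1). Most of these are days on which no visit is scheduled, so the count does not measure lost data. Nothing in the documents shows that late visits are late because of toxicity.
- **Origin.** The mismatch begins in Protocol Table 5, which puts a ±7 scan in a ±3 column. That explains the SAP's window but does not resolve the conflict, since the SAP carries footnote 15 as well.

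What the reply does not answer is the C3D1 scan itself. The SAP says that visits are recalculated, gives that scan too narrow a window, and offers no fallback.

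**Conclusion.** The point holds for one assessment, the C3D1 tumour scan. Eight of its 15 protocol-allowed days fall in no analysis window. The 53% is a share of calendar days; the documents give no distribution of scan dates, so the share of scans affected is unknown.

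The definite consequence is limited to by-visit tumour outputs. An effect on BOR, ORR and CBR is conditional on reading a visit response as a windowed visit, and would then be 5 percentage points for each patient whose classification changes, assuming 20 treated patients in the group. That PFS and duration of response are unaffected assumes they are derived from actual scan dates, as their definitions imply.

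It would be wrong to conclude that the SAP windows are narrower in general. From C5 onward both documents use ±7, and the safety-visit windows match the protocol. The point should be corrected because the SAP contradicts its own schedule and the remedy is almost free, but it does not threaten the trial's main results.

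**What to change.** In SAP 6.2.2:

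1. Add a separate tumour-assessment window for C3D1 of day 50–64 (57 ± 7). All 15 allowed scan days are then covered, with no overlap with C2D15 (40–46) or C4 (82–88, undelayed cycles).
2. State the scheduled study day for each visit from C4 onward, so that the ±3 and ±7 windows have an anchor.
3. State that BOR and best change from baseline use every post-baseline scan up to progression, by actual date and regardless of window. This also covers later scans that drift outside a nominal window.

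Leave the safety windows as they are. Contiguous midpoint windows would be a different convention, would bring unscheduled tests into tables meant for scheduled visits, and are not needed to resolve this conflict.

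The cost is a few lines of SAP text and minor programming. No change to data collection or trial conduct is required.
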